6.3. Safety Analysis Set

The safety analysis set will include all patients who receive any study medication, even if they vomit shortly after administration or are unable to swallow the medication.

6.4. Treatment Misallocations

If a subject is randomized but took incorrect treatment, then they will be reported under their randomized treatment group for all efficacy analyses, but will be reported under the treatment they actually received for all safety analyses.

6.5. Protocol Deviations

Significant protocol deviations may include, but not limited to:

- Failure to meet significant inclusion/exclusion criteria
- No evidence of adequate compliance to study medication
- Receiving excluded concomitant medication, including additional doses of study medication not administered per protocol
- Failure to obtain required efficacy data:
 - While in ER: patients who sign out AMA or who are otherwise uncooperative in providing protocol-specified efficacy or safety data, including failure to stay in ED for 4 hours following dosing for a follow-up ECG
 - After discharge: patients who fail to provide protocol-specified follow-up data, including data on drug compliance and efficacy assessments

7. ENDPOINTS AND COVARIATES

7.1. Efficacy Endpoint(s)

- 1) Primary Efficacy Endpoint: the proportion of patients who fulfill all the following 3 criteria from 30 minutes after first administration of study medication until 24 hours after the first dose of study medication:
 - a. absence of vomiting
 - b. no use of rescue medication, and
 - c. no intravenous hydration

If all of the above three criteria are fulfilled, the patient is considered a treatment success for the primary analysis. If one or more of the above three criteria are not fulfilled, i.e., the patient either experiences vomiting, receives rescue medication or receives intravenous hydration from 30 minutes through 24 hours after the first dose of study medication, the patient is considered a treatment failure.

Based on the 2nd blinded dry run conducted on [REDACTED], there were 28 subjects who did not have all the information needed to determine per the algorithm used if they met the primary endpoint successfully. For 17 patients, all treated under amendment 1 or 2, in which the primary endpoint was treatment success on emergency department discharge, the reason for not having complete information was the lack of an ER day diary. For these patients, based on all follow up data available, no treatment failure events occurred. Therefore, these patients are considered treatment successes. Among the other eleven, data were reviewed and several queries issued. Based on this review, patients were assessed by the medical monitor to be treatment successes (n=4), failures (n=1) or unknown (n=6). The adjudicated primary endpoint outcomes will be used for the primary analyses.

2) Secondary and Tertiary Efficacy Endpoints:

- Treatment success, as defined above, through 4 days following first dose of study medication
- Proportion of patients who experience or require each of the components of treatment failure:
 - Vomiting
 - Rescue antiemetic therapy
 - Intravenous hydration
- Severity of nausea
- Incidence and severity of diarrhea
- Incidence and severity of other symptoms of gastroenteritis
- Time from first dose of study medication to discharge from ED, extended observation unit or hospital, whichever comes last
- Days to resumption of normal activities (work/school/household)
- Proportion of patients requiring hospitalization
- Proportion of patients returning to emergency department for gastrointestinal symptoms within 4 days of initial discharge

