	
Any patient receiving rescue medication or parenteral hydration will be deemed a treatment failure.
 
Metoclopramide 0.3 mg/kg, maximum dose 10 mg, administered intravenously will be the default rescue medication. Oral metoclopramide or other antiemetics administered either intravenously or orally may be used at the investigator's discretion. However, patients are not to receive ondansetron or other 5-HT3 antagonists by any route for at least 24 hours after administration of study medication. The following 5-HT3 antagonists are available in the US: alosetron (Lotronex), dolasetron (Anzemet), granisetron (Sancuso and others), ondansetron (Zofran, Zuplenz and others), palonsetron (Aloxi).
 
Oral fluids will be administered as tolerated once a patient has not vomited for 30 minutes after dosing with study medication (second dose for those patients receiving 2 doses in the ED). Guidelines for administration of oral fluids are shown on page 20, section 4.4.1, of the protocol.
 
Patients tolerating oral fluids will be discharged once deemed stable by the attending physician but not prior to 4 hours after dosing. On discharge, patients will be given 3 additional doses of study medication to take once daily if necessary.
 
Patients who do not tolerate oral fluids may receive parenteral hydration. Data will be collected daily for up to 4 days following study initiation (until symptoms have resolved) to ascertain whether the patient had further vomiting, other sequelae of the acute gastroenteritis or required further medical care for the gastroenteritis. Data may be collected by entry by the patient or a caregiver into a web-based system or on paper, or by telephone contact daily from a study staff member. If during the follow-up period, symptoms progress or worsen or new symptoms develop, the patient may be asked to return for further evaluation. If by day 4 after discharge (i.e., the day after the last dose of study medication), the patient still notes gastroenteritis symptoms, he or she will be instructed to return for further evaluation.

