## 4. Study Design

### 4.1 Overview

Patients presenting to the emergency department who fulfill entry criteria will be asked to participate. A screening log will be kept listing all patients considered with reasons for patients not entering the study. Any patient whose information is reviewed in consideration for the study, even if not actually approached, is to be included in the screening log. The screening log will differentiate between those who are prescreened, i.e., who are reviewed but never progress to request for consent, from those who are screened, i.e., who are approached for consent, whether or not they actually sign consent or eventually participate in the study. Qualifying patients, once they have signed consent, will be stratified by age ( $\geq$  vs <age 18) and randomized 60:40 to RHB-102 or matching placebo. All patients will undergo laboratory testing and ECG, as specified below, once they have signed consent. However, only results of the pregnancy test (for women of childbearing potential) and a finger stick blood glucose (for patients with type 2 diabetes mellitus controlled by diet or oral medications) are required prior to treatment.

Patients will be started on oral fluids  $\geq$ 30 minutes after taking study medication (second dose for patients who receive 2 doses in ED) if they have not vomited during that period. Intravenous hydration should not be administered unless the patient has vomited or is clearly unable, after a reasonable period of time has elapsed since administration of study medication, to tolerate oral fluids.

At  $4\pm0.25$  hours after initial dosing, all patients are to have a repeat 12-lead ECG. Once stable, but not less than 4 hours after initial dosing, patients may be discharged from the emergency department. If a patient leaves the ED less than 4 hours after dosing, an ECG should be obtained if at all possible, even if the patient is leaving against protocol requirements.

On discharge, patients will be given an additional 3 doses of study medication to take at 24-hour intervals if nausea persists. Patients will be contacted daily for 4 days after discharge to determine their condition. Those patients who have persistent, worsening or recurrent nausea and/or vomiting during the follow-up period may be asked to come in for follow-up assessment by study personnel.

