#### 4.4 Concomitant Therapy

If deemed necessary by the investigator, patients may take rescue antiemetics, either orally or intravenously, as described in section 4.2, above. Also, if deemed necessary by the investigator, patients may receive parenteral hydration. However, every effort should be made to avoid both rescue medications and parenteral hydration, and to proceed with oral hydration, unless it is clear that the patient will not be able to tolerate oral hydration.

**From the time a patient takes any antiemetic other than study medication, whether while in or after leaving the emergency department, or receives parenteral hydration, he or she will be deemed a treatment failure, even in the absence of vomiting.**

Patients may take antipyretic and antidiarrheal medication as needed prior to or after initial dosing with study medication. Patients may also take medications for gastrointestinal symptoms as long as they are not specifically antiemetics. For

example, they may use proton pump inhibitors or antacids. Once vomiting is controlled, patients should resume any medications they routinely take.

Patients for whom an intravenous medication (other than antiemetic) is indicated once on study may receive that medication in up to 100 mL fluid. This will not be considered parenteral *hydration*. For example, if a patient has a urinalysis suggesting infection and the investigator or other physician wish to give the patient an intravenous antibiotic dose, that will not be considered treatment failure as long as the drug is given in ≤100 mL fluid.

If once on study, a patient requires a medication which may prolong the QTc interval, he or she should not receive further study medication. However, evaluation of the patient should continue per protocol.

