#### 4.4.1 Oral hydration guidelines

The following are guidelines for oral rehydration. These are suggested but not required; investigators may follow institutional procedures and should use clinical judgment in determining when and how much oral fluid to administer.

1. After ingestion of the study drug along with small amount of fluids, nothing else by mouth for the first 30 minutes.
2. At approximately 30 minutes after study drug administration, gently encourage drinking of approximately 8 ounces (240 mL) of fluid over the next 30 minutes.
3. At approximately 60 minutes after study drug administration, further encourage oral hydration according to patient symptoms, as follows:
  - a. The overall goal is for the patient to ingest approximately one liter over 1-2 hours after study drug administration. One liter is common, although as much as 2 liters may be taken, depending on the patient's volume status and symptom of nausea.
  - b. Alternatively, a patient may ingest 600-700 mL, indicate feeling better and want to be discharged. If, based on improvement in symptoms, the investigator feels confident the patient will do well at home, the discharge takes place.

Please note the following:

- Too much fluid given too quickly may increase symptoms of nausea.
- Too little fluid: in the absence of at least some ED rehydration, it is difficult to be confident the patient will further tolerate reasonable amounts of fluid at home (or to determine if the patient is failing hydration in the ED).

**From the time a patient takes any antiemetic other than study medication, whether while in or after leaving the emergency department, or receives any parenteral hydration, he or she will be deemed a treatment failure.**

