#### 5.2.2 Observation while in emergency department

To start immediately after administration of study medication:

- Intake and output hourly:
  - all oral and parenteral intake

- urination: number of voidings
  - vomiting: number of episodes
  - stool output: number, consistency (per scale in original protocol and per Bristol Stool Scale, Appendix I)
- Vital signs at least hourly and just prior to discharge: temperature, blood pressure, pulse, respiratory rate
- Questioning regarding adverse events: hourly and just prior to discharge
- Assessments of nausea: on signing informed consent, just prior to first dose of study medication, hourly, just prior to discharge from emergency department. A 5-point Likert scale will be used:
  - 0 No nausea
  - 1 Mild nausea
  - 2 Moderate nausea
  - 3 Severe nausea
  - 4 Nausea as bad as can be

- 12-lead ECG 4±0.25 hours after initial dose of study medication (regardless of whether dose was repeated in ED). If patient leaves ED <4 hours after dosing, an ECG should still be obtained just prior to discharge.
- Brief physical examination of pertinent systems prior to discharge

If a patient vomits ≥30 minutes after taking the first dose of study medication, requires rescue antiemetic or parenteral hydration, he or she will be considered a treatment failure. The patient will be followed according to the schedule above for a total of 4 hours from the time of first administration of study medication or until discharged home, whichever comes first. After that, for patients still in the emergency department or hospital, the patient will be followed per standard protocol, according to the patient's condition.

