#### 5.2.3 Procedures after discharge from emergency department:

Any patient who has a post-dosing ECG showing QTc>500 msec must have a follow-up ECG within 72 hours of initial dosing showing resolution of the QTc prolongation. This may be performed on an inpatient or outpatient basis at the investigator's discretion. If the QTc does not decrease below 500 msec during initial follow-up, the medical monitor must be contacted to discuss further follow-up.

If a patient vomits from 30 minutes after taking the first dose of study medication until 24 hours after the first dose of study medication or requires rescue antiemetic or parenteral hydration during that period, even without vomiting, he or she will be considered a treatment failure. In that case, the only post-emergency department follow-up will be a call 72-96 hours after discharge from the emergency department to ascertain whether the patient's symptoms have

resolved, whether any adverse events occurred, and whether the patient required further medical follow-up, either in an emergency department or other medical facility.

Prior to discharge, patients who are treatment successes (i.e., no vomiting, no rescue medication and no parenteral hydration while in emergency department) will be given a diary card to record:

- all episodes of vomiting and bowel movements, with description of each bowel movement
- severity of nausea (on a 5-point Likert scale) three times a day: before breakfast or the time at which the patient usually eats breakfast, between 1:00-2:00 pm, and at bedtime
- any symptoms the patient may have related to gastroenteritis, such as chills, fever, abdominal pain
- adverse events
- medications taken, either for gastroenteritis (study medication and others) or other conditions

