## 7. Data Analysis and Statistical Considerations

### 7.1 Sample Size Considerations

The primary endpoint is a composite of the following three parameters from 30 minutes until 24 hours after the first dose of study medication:

- absence of vomiting
- no use of rescue medication, and
- no intravenous hydration

If all of the above three criteria are fulfilled, the patient is considered a treatment success for the primary analysis. If one or more of the above three criteria are not fulfilled, i.e., the patient either experiences vomiting, receives rescue medication or receives intravenous hydration from 30 minutes through 24 hours after the first dose of study medication, the patient is considered a treatment failure.

It is expected that approximately 40% of the placebo group will fail treatment during the 24 hours after initial dosing and that RHB-102 will reduce the incidence of treatment failure by approximately 50%, i.e., to an incidence of 20% in the active treatment group. Patients will be stratified by age (<18,  $\geq$ 18 years of age) and randomized 60:40 to active versus placebo. To demonstrate a statistically significant decrease in the incidence of vomiting with a 2-tailed p-value=0.01 and power=90%, 320 patients will be entered into the study, 192 randomized to RHB-102 and 128 to placebo.

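### A patient whose only rescue antiemetic or IV hydration falls in the first 30 minutes is a success under SAP 7.1 and a failure under protocol 4.4; the plan needs one scoring rule

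*SAP*

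**What the plan says.** Two sets of statements define failure.

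The formal endpoint has one window for all three components. Protocol 7.1 says: "The primary endpoint is a composite of the following three parameters from 30 minutes until 24 hours after the first dose of study medication". SAP 7.1 follows it and fails a patient who vomits or "receives rescue medication or receives intravenous hydration from 30 minutes through 24 hours after the first dose of study medication". The synopsis entries for endpoints and statistics, protocol 2.1 and SAP 3.2 agree. So does the failure definition in protocol 5.2.3, which fails a patient who vomits in the window "or requires rescue antiemetic or parenteral hydration during that period, even without vomiting, he or she will be considered a treatment failure".

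The failure rules in the conduct sections have no such start for rescue or hydration. The synopsis methodology says, in bold: "Any patient receiving rescue medication or parenteral hydration will be deemed a treatment failure". Protocol 4.4, also in bold, says that a patient who takes a non-study antiemetic "or receives parenteral hydration, he or she will be deemed a treatment failure, even in the absence of vomiting". Protocol 4.4.1 repeats the rule: "From the time a patient takes any antiemetic other than study medication, whether while in or after leaving the emergency department". Protocol 5.2.2 attaches the 30-minute limit to vomiting and then adds, without a limit, that a patient who "requires rescue antiemetic or parenteral hydration, he or she will be considered a treatment failure".

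**The concern.** A 30-minute allowance is easy to justify for vomiting, because the tablet needs time to act. It is harder to justify for rescue or IV fluid: once either is given, the 24-hour outcome no longer reflects study medication alone. Protocol 4.4 appears to recognise this. SAP 7.1 decides the primary analysis, and it ignores rescue or fluid given before 30 minutes.

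At stake is whether the composite has one meaning. If two passages give opposite scores for the same patient, the result depends on which passage the programmer or adjudicator followed.

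**Working it through.** **1. The plan's own figure.** Inputs from protocol 7.1: failure 40% on placebo and 20% on RHB-102, two-sided 0.01, power 90%, allocation 60:40 (k = 1.5).

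n(placebo) = [z(0.995)·√(p̄(1−p̄)(1+1/k)) + z(0.90)·√(p₁(1−p₁)+p₂(1−p₂)/k)]² / (p₁−p₂)², with p̄ = (0.40 + 1.5×0.20)/2.5 = 0.28.

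This is [2.576×√0.336 + 1.282×√0.3467]² / 0.04, which rounds up to 127 placebo, with 191 RHB-102: 318 in total, against 320 planned. At 128 and 192 patients, power is 90.4% at 0.01 and 97.2% at 0.05, the level at which protocol 7.4.1 tests. The sample size reproduces and does not depend on this point.

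**2. The rules side by side.**

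| Place | Vomiting counts | Rescue and hydration count |
|---|---|---|
| Synopsis endpoints and statistics; protocol 2.1, 5.2.3, 7.1; SAP 3.2, 7.1 | 30 min to 24 h | 30 min to 24 h |
| Synopsis methodology (bold rule) | not addressed | any time; no start or end given |
| Protocol 4.4 and 4.4.1 (bold rule) | not required for failure | any time; no start or end given |
| Protocol 5.2.2 | from 30 min | no start given |

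**3. One patient under both.** Suppose rescue, or a complete infusion above the 100 mL carrier allowance of 4.4, is given before 30 minutes, and there is no event from 30 minutes to 24 hours. SAP 7.1 gives success. Protocol 4.4, 4.4.1, 5.2.2 and the synopsis methodology give failure. No text ranks the two.

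**4. Can it happen?** Rescue is permitted only from 30 minutes (synopsis methodology; protocol 4.2), so earlier rescue is a deviation. For fluid, protocol 4.1 says "Intravenous hydration should not be administered unless the patient has vomited or is clearly unable", after a reasonable time since dosing, to tolerate oral fluids; it sets no minimum time for a patient who has vomited. Protocol 4.2 requires an adequate attempt at oral fluids first. Early hydration is thus restricted, and 4.1 and 4.2 need reconciling with each other.

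**5. Does a planned analysis catch it?** No.
- The ITT set (SAP 6.1) keeps everyone who received any study medication.
- Subgroup Population 1 (SAP 6.2.1) is defined by entry criteria, redosing and discharge diagnosis. Subgroup Population 2 (SAP 6.2.2) is defined by site enrolment.
- The sensitivity analyses in SAP 9.2 vary only how dropouts and unknown outcomes are imputed.

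Protocol 5.2.3 adds a complication. It gives the diary card to patients with no vomiting, rescue or hydration in the ED, again without a 30-minute start. A patient treated early may leave without a diary. If the 24-hour outcome is then unknown, SAP 8 imputes failure.

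**6. Size.** One reclassified patient lowers the RHB-102 success rate by 1/192 = 0.52 points, or the placebo rate by 1/128 = 0.78 points. The number affected is not given. For illustration only, take assumed shares moved from success to failure, starting from 40% and 20%, at 128 and 192 patients:

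| Moved, placebo / RHB-102 | Difference | Power at 0.05 |
|---|---|---|
| 0% / 0% | 20 points | 97.2% |
| 1% / 1% | 20 points | 97.0% |
| 5% / 2% | 23 points | 99.1% |
| 1% / 3% | 18 points | 92.8% |

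The effect can go either way, depending on which arm has more early treatment.

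**The case against.** The strongest reply is that the formal definition is uniform. Every place that defines the primary endpoint as such uses one window for all three components. On this view 4.4, 4.4.1 and the bold synopsis sentence are conduct reminders. They give no end either: read literally, fluid on day 3 would fail a 24-hour endpoint. Much of this stands, and it rules out several stronger readings.

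- A reader might infer that the SAP departed from the protocol. It did not; SAP 7.1 copies the protocol's endpoint. The conflict lies inside the protocol.
- A reader might infer that the synopsis as a whole lacks the window. Only its methodology sentence does.
- A reader might infer that 4.4 prescribes counting from first dose through 24 hours. It states neither limit.
- A reader might take a patient who vomits at 20 minutes and gets fluid at 25 as a certain, protocol-compliant success under SAP 7.1. That sits badly with the oral-fluid attempt in 4.2, since oral fluids start only after 30 minutes without vomiting. An infusion still running at 30 minutes could also be read as received in the window.
- A reader might infer dilution of the treatment effect. Neither its direction nor the share of patients is supported.

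What remains is that the rules without a 30-minute start are bolded and repeated, 5.2.2 limits vomiting alone, and a patient who deviates still has to be scored.

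**Conclusion.** The inconsistency is real but narrow. It concerns patients, mostly protocol deviators, whose only rescue or hydration came before 30 minutes. SAP 7.1 calls them successes and protocol 4.4 calls them failures. The number may be very small or zero, so this does not threaten the planned power or sample size. It does leave the primary endpoint without a single scoring rule for these patients, and no planned analysis would show whether it matters.

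The conclusion rests on comparing the texts. It assumes that the bolded rules are meant to govern scoring, as their wording says, and that an infusion is placed by its start time, which the SAP does not state.

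**What to change.** Reconcile the passages and state one scoring rule in SAP 7.1 and protocol 7.1:

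- Keep the 30-minute start for vomiting.
- Score any rescue antiemetic or IV hydration, outside the 100 mL carrier allowance, as failure from the first dose through 24 hours. This fits the intent of 4.4, but the two limits must be written down because 4.4 does not give them.
- State whether an infusion's start time decides.
- Apply the same start to the 4-day endpoint.
- Report patients given rescue or hydration before 30 minutes, by arm, and repeat the age-stratified CMH test under the other rule as a sensitivity analysis.

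This changes scoring only, not treatment. The supplemental SAP records unblinding on June 3, 2017, so an analysis added after that date should be labelled post hoc and both results shown.

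The cost is a sentence in each document, one derivation and one repeat analysis. Supplemental SAP section 13 already derives times to first rescue and first IV fluid above 100 mL, so the data should be at hand. Success rates may fall slightly, by 0.52 or 0.78 points per affected patient.
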